I agree to comply with the International Council for Harmonisation (ICH) Guideline for Good Clinical Practice (GCP) and applicable Food and Drug Administration (FDA) regulations/guidelines set forth in 21 Code of Federal Regulations Parts 50, 54, 56, and 312 and local regulations per country.

I agree to ensure that the confidential information contained in this document will not be used for any purpose other than the evaluation or conduct of the clinical investigation without the prior written consent of United Therapeutics Corp.

I also have read the current Investigator’s Brochure for UT-15C (treprostinil diethanolamine) and acknowledge that review of the information contained in the Investigator’s Brochure is a requirement for Investigators before using UT-15C (treprostinil diethanolamine) in a clinical study.

Signature of Principal Investigator

Date

Printed Name of Principal Investigator

LIST OF ABBREVIATIONS

6MWD	6-Minute Walk Distance
6MWT	6-Minute Walk Test
AE	Adverse Event
ALT	Alanine Aminotransferase
AST	Aspartate Aminotransferase
BID	Twice daily
C _{max}	Maximum Plasma Concentration
CTD	Connective Tissue Disease
CVD	Cardiovascular Disease
CYP	Cytochrome P450
eCRF	Electronic Case Report Form
EC	Ethics Committee
ERA	Endothelin Receptor Antagonist
FDA	Food and Drug Administration
GCP	Good Clinical Practice
GGT	Gamma-Glutamyl Transferase
GLP	Good Laboratory Practice
HIV	Human Immunodeficiency Virus
H-L	Hodges-Lehmann
ICF	Informed Consent Form
ICH	International Council for Harmonisation
IND	Investigational New Drug
IRB	Institutional/Independent Review Board
IV	Intravenous(ly)
IVRS	Interactive Voice Response System
IWRS	Interactive Web Response System
NTP	National Toxicology Program
NT-proBNP	N-Terminal Pro-Brain Natriuretic Peptide
PAH	Pulmonary Arterial Hypertension
PDE5-I	Phosphodiesterase-5 Inhibitor
PGI ₂	Prostacyclin
SAE	Serious Adverse Event
SC	Subcutaneous
SD	Standard Deviation
sGC	Soluble Guanylate Cyclase Stimulator
TID	3 Times Daily
UT-15C	Treprostinil Diethanolamine
WHO	World Health Organization
WOCBP	Woman of Childbearing Potential

PROTOCOL SYNOPSIS

Title	Open-Label Extension Study of UT-15C in Subjects with Pulmonary Arterial Hypertension - A Long-Term Follow-up to Protocol TDE-PH-310
Study Phase	III
Indication	Pulmonary Arterial Hypertension (PAH)
Primary Objective	
 To provide UT-15C for eligible subjects who participated in Study Protocol TDE-PH-310
Secondary Objective(s)	
 To assess the long-term safety of oral UT-15C To assess the effect of continued long-term therapy with UT-15C on exercise capacity (6-Minute Walk Distance [6MWD]/Borg dyspnea score), World Health Organization (WHO) Functional Class, and N-terminal pro-brain natriuretic peptide (NT-proBNP) (at Week 48 only)
Exploratory Objective	
 Optional evaluation of pharmacogenomics
Study Design	Multi-center, open-label study for eligible patients who participated in TDE-PH-310
Sample Size	Up to 850 subjects from Protocol TDE-PH-310 will be enrolled.
Summary of Subject Eligibility Criteria	Participation and completion of required visits from TDE-PH-310. Discontinued due to clinical worsening in TDE-PH-310. All ongoing subjects at the time the number of adjudicated clinical worsening (morbidity or mortality) events specified in Protocol TDE-PH-310 has occurred will be eligible to participate in this open-label study.
Drug Dosage and Formulation	
All subjects will receive oral treprostinil diethanolamine (UT-15C) sustained release tablets. Study drug will be provided in 0.125, 0.25, 0.5, 1.0, and 2.5 mg sustained-release (SR) tablets to be administered 3 times daily (TID) immediately after (~10 minutes) consuming food.
 
For subjects who were randomly allocated to UT-15C in TDE-PH-310, the initial dose of UT-15C in the open-label study will be based upon their final dose in TDE-PH-310. Dose escalation of UT-15C may occur in either 0.125 or 0.25 mg increments no more than every 24 hours based on adverse effects and signs and symptoms of PAH.
 
For subjects who were randomly allocated to placebo in Protocol TDE-PH-310, dosing of UT-15C will be initiated at 0.125 mg TID. Dose escalations can occur no more than every 24 hours (3 consecutive doses) in 0.125 mg increments TID during the first 4 weeks of the study. Following 4 weeks

	of treatment, dose escalation may occur no more than every 24 hours in either 0.125 mg or 0.25 mg increments TID every 24 hours. There is no maximum dose specified for this study. Note that sudden dose escalations or reductions may lead to intolerable adverse effects or worsening PAH and gradual dose titrations are recommended to reduce the risk to subjects.
Control Group	None
Route of Administration	Oral
Procedures	
Study visits will occur at Baseline, Weeks 6, 12, and every 12 weeks thereafter. Study visits will continue until either UT-15C becomes commercially available within the respective territories, or the study is discontinued by the Sponsor. Study assessments will include:
 
• 6-Minute Walk Test (6MWT)/Borg dyspnea score• WHO Functional Class• NT-proBNP (Week 48 only)• Safety (vital signs, adverse events [AEs], clinical laboratory parameters, concomitant medications)• Optional assessment of pharmacogenomics.
Statistical Considerations	All data will be summarized in tables and listings.
Sponsor	United Therapeutics Corp. [name]

TABLE OF CONTENTS

LIST OF CONTACTS FOR STUDY	2
INVESTIGATOR’S AGREEMENT	3
LIST OF ABBREVIATIONS	4
PROTOCOL SYNOPSIS	5
TABLE OF CONTENTS	7
Table of In-Text Figures	9
1 BACKGROUND AND RATIONALE	10
1.1 DEFINITION OF CLINICAL PROBLEM	10
1.2 TREPROSTINIL DIETHANOLAMINE BACKGROUND	11
1.2.1 General Pharmacology	11
1.2.2 General Toxicology	12
1.2.3 Clinical Pharmacology	15
1.2.4 Efficacy and Safety Data	18
1.3 RATIONALE FOR DEVELOPMENT OF STUDY DRUG IN DISEASE/CONDITION	23
1.4 CLINICAL HYPOTHESIS	24
2 OBJECTIVES	24
2.1 PRIMARY OBJECTIVE	24
2.2 SECONDARY OBJECTIVES	24
2.3 EXPLORATORY OBJECTIVE	24
3 EXPERIMENTAL PLAN	24
3.1 STUDY DESIGN	24
3.2 OVERALL SCHEDULE OF TIMES AND EVENTS	25
3.3 CLINICAL ASSESSMENTS	26
3.3.1 Efficacy	26
3.3.1.1 Six-Minute Walk Test	26
3.3.1.2 Borg Dyspnea Score	26
3.3.1.3 WHO Functional Class	26
3.3.1.4 N-terminal proBNP	26
3.3.1.5 Optional Pharmacogenomics	26
3.3.2 Safety	27
3.3.2.1 Vital Signs	27
3.3.2.2 Physical Examination	27
3.3.2.3 Clinical Laboratory Assessments	27
3.3.2.4 Adverse Event Assessments	27
3.3.2.5 Concomitant Medications	28
3.4 NUMBER OF CENTERS	28
3.5 NUMBER OF SUBJECTS	28
3.6 ESTIMATED STUDY DURATION	28

4	SUBJECT ELIGIBILITY	29
4.1	INCLUSION CRITERIA	29
4.2	EXCLUSION CRITERIA	29
4.3	PRESCRIBED THERAPY.....	30
4.3.1	Concomitant Medications	30
5	SUBJECT ENROLLMENT	30
5.1	TREATMENT ASSIGNMENT	30
5.2	RANDOMIZATION	30
5.3	BLINDING.....	30
6	DRUGS AND DOSING (OR TREATMENT PROCEDURES)	30
6.1	DRUG DOSAGE, ADMINISTRATION AND SCHEDULE	30
6.2	ACCESS TO BLINDED TREATMENT ASSIGNMENT	31
6.3	COMPLIANCE	32
7	EXPERIMENTAL PROCEDURES	32
7.1	TREATMENT PHASE.....	32
7.1.1	Baseline/Study Entry.....	32
7.1.2	Week 6 Visit	34
7.1.3	Week 12 Visit	34
7.1.4	Follow-up Visits (every 12 weeks).....	35

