TDE-PH-304 is a long-term, open-label, international, Phase 3 studies designed to provide access to UT-15C for subjects previously enrolled in studies TDE-PH-301, TDE-PH-302, TDE-PH-308, or other specified studies conducted during the UT-15C development program. Secondary objectives of the study are to assess the long-term safety of UT-15C in PAH patients and to assess the effect of continued therapy on exercise capacity via 6MWD following one year of treatment with UT-15C. As of 01 September 2015, over 896 subjects were enrolled, representing 2377.7 patient-years of exposure. The mean and maximum duration of exposure was 138.8 and 444.9 weeks (2.66 and 8.53 years), respectively. The mean dose of oral treprostinil achieved was 3.9, 4.5, 4.8, 5.0, 5.5, 5.9, and 5.9 mg BID at 1 year (N=605), 2 years (N=472), 3 years (N=337), 4 years (N=230), 5 years (N=119), 6 years (N=77), and 7 years (N=37), respectively. Adverse Events were typical of prostacyclin

therapy; laboratory findings were unremarkable and did not suggest any specific safety concerns related to long-term treatment with UT-15C. Following 12 months of oral treprostinil treatment, the mean 6MWD increased by +25 meters as compared with Baseline. Kaplan-Meier analysis of subject survival demonstrated 1-, 2-, and 3-year survival estimates of approximately 93.6%, 87.9%, and 82.2%, respectively.

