3.2 OVERALL SCHEDULE OF TIMES AND EVENTS

Study Timeline	Baseline ^b (Study Entry)	Week 6 ^c	Week 12 ^c	Follow-up Visits (every 12 weeks) ^c	Study Termination Visit ^k
Informed consent	X				
Inclusion/exclusion criteria	X				
Vital signs ^a	X	X	X	X	X
Physical examination	X				X
6MWT / Borg dyspnea score ^d	X	X	X	X	X
WHO Functional Class	X	X	X	X	X
Clinical laboratory assessments	X		X	X ^e	X
Urine pregnancy test ^f	X	X	X	X	X
Dose titration	X	X	X	X	
NT-proBNP	X			X ^g	
Drug accountability/ Compliance	X	X	X	X	X
AEs	X ^h	X	X	X	X ⁱ
Concomitant medications	X	X	X	X	X
Phone calls ^j	X	X	X	X	X
Pharmacogenomic Sample (Optional)				X ^l	X ^l

Abbreviations: 6MWT, 6-Minute Walk Test; AE, adverse event; NT-proBNP, N-Terminal pro-brain natriuretic peptide; WHO, World Health Organization

^a Vital signs should be conducted following at least 5 minutes of rest and prior to or at least 30 minutes following the corresponding 6MWT.

^b Baseline/study entry assessments (6MWT/Borg dyspnea score, WHO Functional Class, clinical laboratory parameters, NT-proBNP, vitals, and physical examination) for this study are those collected at the Study Termination Visit from Study TDE-PH-310 and prior to initiation of open-label study drug. Informed consent and inclusion/exclusion criteria are exclusive to this Protocol.

^c Visit windows are ±14 days.

^d 6MWT must be conducted 3 to 6 hours after the last dose of UT-15C. Subject should rest for 5 minutes prior to each 6MWT.

^e During the follow-up visits, clinical laboratory samples should be collected at the first Follow-up Visit and every other Follow-up Visit thereafter.

^f If applicable, for women of child-bearing potential (WOCBP).

^g NT-proBNP should only be collected at the Follow-up Visit # 3 (Week 48).

^h Any AEs that are ongoing at the Study Termination Visit from Study TDE-PH-310 should be recorded as continuing AEs in this open-label study.

ⁱ Any AEs that are ongoing at the Study Termination Visit from Study TDE-PH-311 should be followed for up to 30 days after completion of the Study Termination Visit.

^j Phone calls to the subject should occur at least weekly for the first 12 weeks, and at least monthly thereafter.

^k After the Study Termination Visit is completed, subjects should down titrate the study drug over an appropriate period of time in accordance with their clinical condition. Once the study drug has been discontinued, any remaining supplies should be returned to the clinic for drug accountability.

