4 SUBJECT ELIGIBILITY

4.1 INCLUSION CRITERIA

A subject is eligible to participate in this study if all of the following criteria apply:

1. The subject voluntarily provides informed consent to participate in the study.
2. The subject participated in Study TDE-PH-310 and met the definition of clinical worsening (as specified in Protocol TDE-PH-310), remained on study drug, was compliant with study procedures and assessments during the TDE-PH-310 Study or was currently enrolled in that study at the time the study was discontinued by the Sponsor.
3. All WOCBP must practice true abstinence from intercourse when it is in line with their preferred and usual lifestyle, or use 2 different forms of highly effective contraception for the duration of the study, and for at least 30 days after discontinuing study medication. Medically acceptable forms of effective contraception include: (1) approved hormonal contraceptives (such as birth control pills), (2) barrier methods (such as a condom or diaphragm) used with a spermicide, (3) an intrauterine device, or (4) partner vasectomy. For women of childbearing potential, a negative urine pregnancy test is required at Baseline (study entry) prior to initiating study medication. WOCBP includes any female who has experienced menarche and who has not undergone successful surgical sterilization (hysterectomy, bilateral tubal ligation, or bilateral oophorectomy) or is not postmenopausal (defined as amenorrhea for at least 12 consecutive months).
4. Males participating in the study must use a condom during the length of the study, and for at least 48 hours after their last dose of study medication.

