4.2 EXCLUSION CRITERIA

A subject is not eligible to participate in this study if any of the following criteria apply:

1. The subject is pregnant or lactating.
2. The subject has received infused or inhaled prostacyclin therapy for 29 days or more.
3. The subject was prematurely discontinued from Study TDE-PH-310 for reasons other than a clinical worsening event.
4. The subject developed a concurrent illness or condition during the conduct of TDE-PH-310 which, in the opinion of the Investigator, would represent a risk to overall health if they enrolled in this study.

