7 EXPERIMENTAL PROCEDURES

7.1 TREATMENT PHASE

7.1.1 *Baseline/Study Entry*

All data collected at the subject's Study Termination Visit during TDE-PH-310 and prior to initiating open-label study drug will serve as Baseline/Study Entry assessments for this study. Following completion of the Study Termination assessments for a subject and entry of required data into the interactive voice or web response system (IVRS/IWRS), the site

personnel will be unblinded to that subject's treatment assignment. Subjects must sign an ICF and meet inclusion/exclusion criteria specific to this protocol. The recommended sequence of events for Baseline/Study Entry is displayed below:

- Informed consent (prior to any study assessments)
 - Inclusion/exclusion criteria
 - Vital signs (following at least 5 minutes of rest)*
 - Physical examination*
 - WHO Functional Class*
 - AE assessment*
 - 6MWT/Borg dyspnea score (for subjects randomized to UT-15C in TDE-PH-310, the 6MWT to be initiated 3 to 6 hours after the last dose of UT-15C; 6MWT to be conducted following at least 5 minutes of rest; Borg dyspnea score to be conducted immediately following 6MWT)*
 - Urine pregnancy test (for WOCBP)*
 - Clinical laboratory assessments*
 - Plasma NT-proBNP*
 - Study drug dosing (for subjects randomized to placebo in TDE-PH-310, the initial dose of UT-15C in TDE-PH-311 should be taken at the study site)
 - Drug accountability
 - Concomitant medications*
 - Weekly telephone calls are highly recommended especially after any dose changes
- *assessments conducted during the Study Termination Visit for the TDE-PH-310 study will not need to be repeated*

The AEs that were ongoing at the end of the TDE-PH-310 study will be recorded as ongoing events for this open-label study. Concomitant medications that were ongoing at the TDE-PH-310 Study Termination Visit will be recorded in the eCRF for the open-label study. Once the subject signs the ICF for this study, all ongoing AEs must be recorded and documented on the eCRF. All AEs and concomitant medications will be reported continuously for the duration of the study. Phone calls to the subject must begin within 1 week of the subject receiving the first dose of study drug and continue to be made weekly for the first 12 weeks of the study. After the first 12 weeks, phone calls must be made at least monthly. Dose titration should occur as needed in accordance with Section 6.1.

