3 STUDY DESIGN

This is an open-label study. Subject visits will occur at Baseline, Weeks 6 and 12, and every 12 weeks thereafter. The study will continue until either oral UT-15C becomes available within the respective territories or the study is discontinued by the Sponsor. The Baseline Visit corresponds to the Study Termination Visit from the parent study (TDE-PH-310) and occurs prior to initiation of the open-label study.

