10 EFFICACY ANALYSES

10.1 6-MINUTE WALK TEST

The listing of the 6MWT will be organized by treatment group in the parent study, and will include subject number, analysis visit, assessment date/time (day), last UT-15C dose date/time (day), the last UT-15C dose (in milligrams), hours from last UT-15C dose to 6MWT, 6MWD results, Borg dyspnea scores, use of supplemental oxygen, and any circumstances affecting the 6MWT. The summaries of 6MWD will be provided by treatment assignment in the parent study (UT-15C or placebo) by visit, PAH etiology (idiopathic, heritable, associated with connective tissue disease, and other), Baseline WHO Functional Class, and quartiles of the last UT-15C dose. The summaries will include descriptive statistics for 6MWD measure at each analysis visit and the change from Baseline. Baseline is defined as the last 6MWD measured prior to the first dose of UT-15C in the TDE-PH-311 study.

Achievement of a walk distance of at least 440 m by each analysis visit will be summarized by treatment group in the parent study and overall. Achievers and non-achievers will then be summarized based on their Baseline walk (≤ 440 m vs >440 m) by treatment group in the parent study and overall.

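### Subjects who enter after clinical worsening take their Baseline at the visit where they left TDE-PH-310, so rebound or recovery is pooled into change from Baseline on UT-15C

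*Protocol*

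**What the plan says.** **Entry.** The eligibility summary in the Protocol Synopsis lists "Discontinued due to clinical worsening in TDE-PH-310" as a way in. Inclusion criterion 2 (Protocol 4.1) covers a subject who "participated in Study TDE-PH-310 and met the definition of clinical worsening (as specified in Protocol TDE-PH-310), remained on study drug", and leaves the definition of worsening to the parent protocol. Exclusion criterion 3 (Protocol 4.2) bars entry if "The subject was prematurely discontinued from Study TDE-PH-310 for reasons other than a clinical worsening event". Worsening is therefore the one reason for leaving the parent study early that still permits entry. The Synopsis also admits subjects still ongoing when the parent study reaches its event count.

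**Baseline.** Under the schedule in Protocol 3.2, the entry assessments "for this study are those collected at the Study Termination Visit from Study TDE-PH-310 and prior to initiation of open-label study drug". Protocol 7.1.1 adds that "assessments conducted during the Study Termination Visit for the TDE-PH-310 study will not need to be repeated". SAP 3 agrees: "The Baseline Visit corresponds to the Study Termination Visit from the parent study (TDE-PH-310) and occurs prior to initiation of the open-label study". Neither document describes a stabilisation period or a second entry measurement.

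**Analysis.** For the walk test, SAP 10.1 states that "Baseline is defined as the last 6MWD measured prior to the first dose of UT-15C in the TDE-PH-311 study". SAP 10.2 and 10.3 use the same rule for Borg score and WHO Functional Class. All three sections report values by visit and change from Baseline. SAP 8 presents tables by parent-study arm and overall. SAP 10.1 also splits 6MWD by etiology, Baseline Functional Class and quartile of last dose. No table is split by route of entry, and SAP 8.1 offers only unspecified exploratory subgroups.

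**The concern.** A secondary objective (Protocol 2.2, SAP 2.1) is to assess the effect of continued UT-15C on exercise capacity and Functional Class. A worsening entrant's reference value comes from the visit at which the subject left because of deterioration. If that value is temporarily low, later values rise without any drug effect, and nothing in an uncontrolled study separates the two.

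Three mechanisms could produce such a rise:

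- regression to the mean, where 6MWD itself was part of the criterion;
- recovery from the event;
- response to PAH therapy added around that time, which Protocol 4.3.1 leaves unrestricted apart from permanent prostacyclin or analogue therapy.

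Former placebo subjects are affected too, because their first UT-15C dose falls at the same point. The share of worsening entrants may also differ between parent arms. Protocol 1.4 hypothesises that UT-15C delays worsening; if so, the former placebo column would contain more of them, and the two columns would be distorted unequally.

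**Working it through.** The plan states no figure to reproduce: there is no sample size calculation, hypothesis test or expected change. What follows is an illustration, and every input to it is an assumption.

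**Inputs**

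- Criterion: the TDE-PH-310 definition is not in the documents. The only walk criterion they describe is the one for TDE-PH-302 (Protocol 1.2.4), a fall of at least 20% together with a new approved PAH therapy. Only the walk part is modelled. Earlier trials had mean Baseline walks of 346, about 330 and 333 m; taking 340 m, the threshold is 0.20 × 340 = 68 m.
- Walk-to-walk SD, s: 20, 30 or 40 m.
- SD of true change, σ: 40, 60 or 80 m.
- Mean true change, m: 0, −20 or −40 m.
- The Baseline walk is the walk that qualified the subject.

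**Model.** Observed change is C = d + e1 − e0, with true change d and walk errors e0 and e1. A subject is selected if C ≤ −68. With S² = σ² + 2s², z = (−68 − m)/S and λ = φ(z)/Φ(z), the expected rise at the next walk, with no treatment effect and no further true change, is

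rebound = −E[e1 | selected] = (s²/S²) × S × λ.

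| s | σ | m | S | z | λ | S × λ | s²/S² | Rebound (m) |
|---|---|---|---|---|---|---|---|---|
| 20 | 80 | −40 | 84.85 | −0.330 | 1.019 | 86.5 | 0.0556 | 4.8 |
| 30 | 60 | −20 | 73.48 | −0.653 | 1.255 | 92.2 | 0.1667 | 15.4 |
| 40 | 40 | 0 | 69.28 | −0.981 | 1.510 | 104.6 | 0.3333 | 34.9 |

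The first and last rows are the extremes of the 27 combinations. At s = 30 m the range is 10.0 to 25.6 m.

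**Sensitivity to the model.** A simulation used true walks with mean 340 m and SD 90 m, the same s, an exponential true decline with mean 0 to 60 m, and selection on a 20% fall. It gave about 6 to 51 m. The form of the model matters as much as its inputs.

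**Effect on a pooled row.** This is share × rebound. The documents give no share. At an assumed 30%, the result is 0.30 × 5 = 1.5 m to 0.30 × 35 = 10.5 m. The share need not be constant. As the criteria read, ongoing subjects become eligible only when the parent study closes, so the data cut that SAP 5 plans for that time would lean towards worsening entrants.

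**If the termination walk is not the qualifying walk.** Its error is then independent of the selection, so its expected value is zero and the walk-error rebound disappears. Recovery and new therapy remain, and the documents give no basis for sizing either.

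**Scale.** For the earlier extension, TDE-PH-304, Protocol 1.2.4 reports: "Following 12 months of oral treprostinil treatment, the mean 6MWD increased by +25 meters as compared with Baseline".

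**The case against.** The case on the other side is substantial, and much of it stands.

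- **The metre figures are conditional.** They need a walk-based criterion and a Baseline that is the qualifying walk; the documents establish neither. The TDE-PH-302 definition also includes death, transplantation, septostomy and PAH hospitalization, and couples its walk component with new therapy. Subjects who qualify through a non-walk event are not selected on 6MWD, so the formula does not apply to them. This stands.
- **Direction.** A reader might infer that the bias always favours UT-15C. The documents do not show that. Exclusion criterion 2 bars infused or inhaled prostacyclin only at 29 days or more, so shorter use before entry is possible and could raise the termination-visit value. Disease progression also pulls later values down, so net change need not be positive. A tendency is all that can be claimed.
- **Other summaries.** A reader might infer that change from Baseline is the only efficacy measure. It is not: SAP 10.1 also gives the walk at each visit and achievement of 440 m by visit.
- **Removing worsening entrants from the overall row.** This would depart from SAP 7, which bases all analyses on the safety population, and would leave a row selected for not having had the event. The objection to that remedy stands.
- **Descriptive status.** The primary objective is drug access, no test is planned, and all data are listed. This limits the severity. It does not tell the reader of an overall mean change that part of it starts from an exit visit for worsening.

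**Conclusion.** The structure is established by the documents: entry because of worsening, Baseline at the exit visit with no repeat required, uncontrolled change from that value, and no separation by route. Any rebound, recovery or response to added therapy is therefore included in the reported change and would tend to favour UT-15C.

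The size is not established. About 5 to 35 m among worsening entrants is an illustration that holds only if a fall of about 68 m was the criterion, Baseline was the qualifying walk, and the assumed SDs and mean changes apply. A reader might infer that a gain of the size seen in TDE-PH-304 would be an artefact; the documents do not support that.

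This concerns the interpretation of a secondary objective, not a test. It is worth correcting because the correction is cheap.

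**What to change.** In SAP 10.1 to 10.3:

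1. Keep the planned overall and by-arm summaries on the safety population.
2. Add rows by entry route (clinical worsening, or ongoing at parent-study close) to the main by-visit tables 14.2.1.1, 14.2.1.2 and 14.2.1.8. Route is fixed before the first open-label dose, so the split does not condition on later outcome.
3. For worsening entrants, add a supplementary change from the last scheduled parent-study value before the event, or from the TDE-PH-310 Baseline. Name one choice in advance. The split alone is not enough, because it still measures these subjects from the exit value.
4. Footnote all six change-from-Baseline tables (14.2.1.1 to 14.2.1.5 and 14.2.1.8) to say that these subjects' Baseline was taken at exit for worsening.

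**Cost.** SAP wording, extra rows, and a merge of parent-study walk, Borg and Functional Class values that the sponsor should already hold; SAP 9.1 already combines exposure across the two studies. No visit or procedure changes. The drawback is that the supplementary column includes decline during the parent study, some of it on placebo. It must be labelled as such and read beside change from the TDE-PH-311 Baseline, not instead of it.
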